5. ANALYSIS SAMPLES

The Efficacy Population will include all patients who are randomized in the study and dispensed study drug during the Treatment Period.

The Safety Population will include all patients who receive study drug during the Treatment Period.

The Per Protocol Population will include all patients in the Efficacy Population who were dosed according to protocol and have no major protocol deviations. Inclusion in the Per Protocol Population will be determined prior to breaking the study blind. Further details on the identification of major protocol deviations are provided in Section [7.1](#).

In the event patients incorrectly receive treatment associated with a different treatment group, they will be analyzed “as randomized” for efficacy and “as treated” for safety.

6. STUDY SUBJECTS

6.1. Disposition of Subjects

Disposition will be summarized by randomized treatment group and overall for all patients screened in the study. The following disposition information will be summarized (percentages based on the number randomized, with the exception of the reasons for discontinuation):

- The number of patients screened. Patients who rescreened will be counted only once.
- The number of patients randomized.
- The number and percentage of randomized patients within the Efficacy, Safety, and Per Protocol Populations.
- The number and percentage of patients who completed treatment, defined as patients with either “Complete-Entering Open Label” or “Complete” noted for the question “Subject Status” on the *Treatment Discontinuation/Completion* electronic case report form (eCRF) page.
- The number and percentage of patients who completed treatment and enrolled in the Open Label Extension, defined as patients with “Complete-Entering Open Label” noted for the question “Subject Status” on the *Study Treatment Discontinuation/Completion* eCRF page.
- The number and percentage of patients who completed treatment and completed the follow-up visit (for those patients who did not enroll in the Open Label Extension), defined as patients with “Complete” noted for the question “Subject Status” on the *Treatment Discontinuation/Completion* eCRF page.
- The number and percentage of patients who prematurely discontinued treatment, and the frequency and percentage of each discontinuation reason. The denominator for the percentage of each discontinuation reason will be the number of patients who discontinued treatment.
- The number and percentage of patients who completed the study, defined as patients with either “Complete-Entering Open Label” or “Complete” noted for the question “Subject Status” on the *Study Discontinuation/Completion* eCRF page.
- The number and percentage of patients who completed the study and enrolled in the Open Label Extension, defined as patients with “Complete-Entering Open Label” noted for the question “Subject Status” on the *Study Discontinuation/Completion* eCRF page.
- The number and percentage of patients who completed the study and who did not enroll in the Open Label Extension, defined as patients with “Complete” noted for the question “Subject Status” on the *Study Discontinuation/Completion* eCRF page.
- The number and percentage of patients who prematurely discontinued the study, and the frequency and percentage of each discontinuation reason. The denominator for the percentage of each discontinuation reason will be the number of patients who discontinued the study.

The number and percentage of patients randomized within each treatment group will also be summarized by investigative site.

Disposition and patient visits will also be presented for each patient in patient data listings. Disposition patient data listing will list date of informed consent, date of first/last treatment, date of end of treatment/early treatment termination, date of end of study/early study termination, and reasons for treatment or study discontinuation. A Kaplan Meier curve of time to early treatment termination for any reason will also be presented for the Safety Population. Patients who have completed treatment will be censored at date of last treatment. Screen failures will be provided in a separate listing. Rescreened patients who later enrolled will not be listed as screen failures.

6.2. Demographic and Other Baseline Characteristics

Demographic characteristics (ie, sex, ethnic origin, race, date of birth, and calculated body mass index) will be collected at the Screening Visit, between Day -28 and -1, and detailed on the eCRF. Demographic characteristics will be summarized using descriptive statistics for all randomized patients by treatment group and overall.

Baseline characteristics will be summarized using descriptive statistics for all randomized patients by treatment group and overall and will include the following:

- baseline total SALT score
- Alopecia areata classification (randomization strata via IWRS): partial scalp hair loss (SALT \geq 50 and $<$ 95); complete or near-complete scalp hair loss (SALT \geq 95)
- duration of current episode in years (calculated as: [date of randomization – date of current episode onset + 1] / 365.25)
- current nail involvement: yes; no (collected via eCOA system as ‘HAND IMAGE CAPTURE’)
- nasal hair involvement: yes; no (collected on the Physical Examinations eCRF page)
- eyebrow involvement: yes; no (collected as part of the BETA assessment)
- eyelash involvement: yes; no (collected as part of the BELA assessment)
- whether the patient has experienced any past and/or concomitant diseases, conditions, or exposures to serious infections such as HIV, or past surgeries: yes; no (collected via the Medical History Summary eCRF page)

Other co-morbidities may be identified and included as baseline characteristics.

All demographics and baseline characteristics will also be listed within a by-patient data listing for all randomized patients.

6.3. Prior and Concomitant Medications

Concomitant medications will be recorded in the eCRF from Screening through study completion at Week 24 or the Follow-Up Visit at Week 28. All medications will be coded using the WHO Drug Dictionary Version 2020-SEP.

Medications are classified as prior if the medication started and stopped prior to the first dose date of study drug or as concomitant if used on or after the first dose date of study drug.

Prior and concomitant medications will be summarized with counts and percentages separately for the Safety Population by treatment group, WHO Drug ATC classification level 2 and preferred term. For each summary, a subject will be counted only once for each medication.

Partial and completely missing dates will be imputed for the purposes of classifying concomitant medications as follows:

- Partial dates will be imputed following the same algorithm as in Section 9.3 for Treatment-emergent adverse events (TEAEs).
- For an entirely missing stop date (ie day, month, and year are missing), the medication will be treated as ongoing.

Prior and concomitant medications will also be listed by-patient.

6.4. Medical History

Medical history will be coded with the MedDRA terminology Version 23.1 and summarized as counts and percentages for the Safety Population by treatment group, system organ class, and preferred term. A patient will be counted only once for each condition. Conditions will be listed, including the verbatim investigator description of the relevant medical condition, the coded terms (system organ class, preferred term), start date, end date, and whether or not the condition is ongoing.

7. STUDY OPERATIONS

7.1. Protocol Deviations

A protocol deviation is any noncompliance with the clinical trial protocol or International Council for Harmonization of Technical Requirements for Pharmaceuticals for Human Use Good Clinical Practice requirements. The noncompliance may be either on the part of the participant, the investigator, or the study site staff. Protocol deviations will be recorded on the source documents and with an explanation for the deviation. All protocol deviations will also be recorded as specified in the monitoring plan.

Protocol deviations will be identified by site staff, through medical reviews, and by clinical research associates during site monitoring. A data review will be conducted before database lock by the sponsor to classify protocol deviations as minor or major. Deviations that may alter or confound interpretation of the study results will be classified as major deviations. Protocol deviations will be summarized as counts and percentages by treatment group, deviation severity, and category for all randomized patients. Deviations will also be presented by patient in a data listing for all randomized patients.

7.2. Randomization

Approximately 700 patients are planned to be randomized in the study. Patients will be randomized in a 3:5:2 ratio (12 mg BID:8 mg BID:placebo) to each of three study arms:

- CTP-543 12 mg BID
- CTP-543 8 mg BID
- Placebo BID

Randomization will be stratified by scalp hair loss into one of the following two categories: 1) Partial scalp hair loss (SALT \geq 50 and $<$ 95); 2) Complete or near-complete scalp hair loss (SALT \geq 95). The randomization schedule will be generated prior to study start.

All study patients, Investigators, and site study staff will be blinded to study drug assignment for the duration of the study. Tablets and packaging of CTP-543 and placebo will be identical in appearance.

A by-patient listing of randomized treatment group and randomization number will be presented.

7.3. Measures of Treatment Compliance

Patients will strive for 100% compliance with the daily dosing schedule. Treatment compliance will be summarized as percent of planned dose received for each dosing regimen. Percent of planned dose received will be calculated for the entire treatment period as follows:

100*(Tablets Dispensed-Tablets Returned)/(Tablets Expected)

Tablets Expected is defined as the time on treatment multiplied by the expected number of pills taken daily (x2 for the 12 mg BID group; x2 for the 8 mg BID group; x2 for the placebo group), where time on treatment is defined as treatment end date – treatment start date + 1. Dose interruptions will be ignored in this calculation. Derived patient compliance, compliance per the

Concert Pharmaceuticals, Inc.
Statistical Analysis Plan – CP543.3001

eCRF (80% or higher versus less than 80%), and dosing exceptions will be listed in by-patient data listings.

For patients who roll over into one of the open label extension studies, it will be assumed that only 1 dose of study drug was administered for the last dose of study drug. For patients who do not roll over, it will be assumed that 2 doses of study drug were administered for the last dose of study drug.

8. ENDPOINT EVALUATION

8.1. Overview of Efficacy Analysis Methods

8.1.1. Multicenter Studies

Patients will be enrolled at up to 70 sites; site identifiers will be included in by-patient listings.

8.1.2. Assessment Time Windows

The visit schedule for all study assessments is provided in Appendix 15.2. Patients will be considered completed for efficacy analyses after Week 24 (Visit 9). Patients will either complete treatment at Week 24 and have a safety follow-up visit at Week 28 (Visit 10) prior to exiting the study, or if eligible, may enroll into an open-label extension study of CTP-543 at their Week 24 visit.

Generally, for scheduled visits where valid assessments were obtained, there will be no reassignment of the analysis visit based on date, and all data will appear in summary tables based on the nominal timepoint. For safety parameters, an unscheduled visit may take priority over a scheduled visit if the unscheduled visit was performed due to invalid collection.

Unscheduled visits and early termination visits will be reassigned based on the analysis windows in the below table and the schedule of events. Assessments may only be re-assigned to visits where they were to be collected per the schedule of events. If an assessment was already documented at that visit, the scheduled data will be used in summaries. If the scheduled data were missing or invalid, then the re-assigned unscheduled visit/early termination visit will be used in summaries. All visits will be included in by-patient data listings.

Table 2: Analysis Windows for Unscheduled and Early Termination Visits

Nominal Visit	Safety Analyses			Efficacy Analyses		
	Lower	Target	Upper	Lower	Target	Upper
Screening	-28	-1	-1	-28	-1	-1
Visit 2-Randomization	1	1	1	1	1	1
Visit 3-Week 2	2	15	22	12	15	18
Visit 4-Week 4	23	29	43	26	29	32
Visit 5-Week 8	44	57	71	54	57	60
Visit 6-Week 12	72	85	99	82	85	88
Visit 7-Week 16	100	113	127	110	113	116
Visit 8-Week 20	128	141	155	138	141	144
Visit 9-Week 24	156	169	183	166	169	172
Visit 10-Week 28	184	197	211	194	197	200

8.1.3. Timing of Analyses

All final, planned analyses will be performed after the last patient has completed all study assessments, all relevant study data have been processed and integrated into the analysis database, and the database has been locked.

Any post hoc, exploratory analyses completed to support planned study analysis, which were not identified in this SAP, will be documented and reported in appendices to the CSR. Any results from these unplanned analyses (post hoc) will also be clearly identified in the text of the CSR.

8.1.4. Multiple Comparisons/Multiplicity

Hierarchical testing will be used to control for multiple comparisons (Figure 1). For the primary efficacy analysis and the key secondary efficacy analyses, a ≤ 0.025 (two-sided) alpha-level will be allocated to each dose for comparison with placebo to adjust for multiplicity of testing associated with two doses. Once $p>0.025$ is observed for a treatment group comparison, inference for additional endpoints is no longer alpha-level protected for that dose group; however, nominal p-values will still be reported.

Subsequently, conditional upon significance (≤ 0.025) for the primary endpoint and first key secondary endpoint for each dose, a linear hierarchical testing approach with ≤ 0.025 (two-sided) alpha-level will be used to test the remaining key secondary endpoint comparisons versus placebo. Once $p>0.025$ is observed for a treatment group comparison, inference for additional endpoints is no longer alpha-level protected for that dose group; however, nominal p-values will still be reported.

All other statistical tests outside of the hierarchy will be carried out at a two-sided significance level of ≤ 0.05 . Nominal p-values will be presented without adjustment for multiple comparisons.

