12. STATISTICAL METHODS

12.1. Sample Size Rationale

Power is calculated for the Primary Efficacy Endpoint for the chi-square test using a 2-sided significance level of 0.025. Based on Phase 2 results, the percentage of patients achieving an absolute SALT score ≤ 20 at Week 24 is assumed to be 40%, 25%, and 10% for the CTP-543 12 mg, CTP-543 8 mg BID, and placebo groups, respectively. Patients will be randomized in a 3:5:2 ratio with a total N of approximately 700 patients (i.e., 210 for 12 mg BID, 350 for 8 mg BID, and 140 for placebo BID). These sample sizes will provide >99% power for the comparison of CTP-543 12 mg BID versus placebo and approximately 94% power for the comparison of CTP-543 8 mg BID versus placebo.

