12.4.3. Multiplicity

Hierarchical testing will be used to control for multiple comparisons. For the primary efficacy analysis and the key secondary efficacy analyses, a ≤ 0.025 (two-sided) alpha-level will be allocated to each dose for comparison with placebo to adjust for multiplicity of testing associated with two doses. The below figure displays the order of testing of the key secondary endpoints. Once $p > 0.025$ is observed for a treatment group comparison, inference for additional endpoints is no longer alpha-level protected for that dose group, however nominal p-values will still be reported.

Subsequently, conditional upon significance (≤ 0.025) for the primary endpoint and first key secondary endpoint for both doses, a linear hierarchical testing approach with ≤ 0.025 (two-sided) alpha-level will be used to test the remaining key secondary endpoint comparisons versus placebo. Once $p > 0.025$ is observed for a treatment group comparison, inference for additional endpoints is no longer alpha-level protected for that dose group, however nominal p-values will still be reported.

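### The 0.025 split between doses is valid, but a dose that wins all six steps cannot pass its 0.025 to the other, so some protected claims are forgone

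*SAP*

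**What the plan says.** SAP 8.1.4 states that a two-sided 0.025 "alpha-level will be allocated to each dose for comparison with placebo to adjust for multiplicity of testing associated with two doses". SAP 8.2 and 8.3 set the order within a dose: SALT score of 20 or less at Week 24, SPRO response at Week 24, then SALT score of 20 or less at Weeks 20, 16, 12 and 8. Every step is at 0.025. At the first p above 0.025, "inference for additional endpoints is no longer alpha-level protected for that dose group; however, nominal p-values will still be reported". Protocol 12.4.3 has the same stopping rule: "inference for additional endpoints is no longer alpha-level protected for that dose group".

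Neither text describes what happens to a dose's 0.025 once all six of its hypotheses are rejected. The two-sided 0.05 in SAP 8.1.4 and 8.4 applies to tests outside the hierarchy, with nominal p-values, so it is not a transfer.

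The two documents differ on the gate before the Week 20 to Week 8 steps. SAP 8.1.4 requires success on the primary endpoint and SPRO dose by dose. Protocol 12.4.3 requires it on both doses. SAP Section 2 gives the SAP precedence where the two differ, but SAP Section 13 does not list this among its changes.

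The testing figure is not visible in the copy reviewed. The reading here rests on the text, which leaves no route to test a dose above 0.025.

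**The concern.** The multiplicity adjustment exists to hold the error across two doses at 0.05. Once every hypothesis for one dose has been rejected, its 0.025 has no further use there. A closed testing procedure can hand it to the other dose, which then continues at 0.05 in the same order. Under the present rule, if 12 mg wins all six steps and 8 mg then stops at SPRO with p = 0.03, that SPRO result is reported as unprotected although the trial had the error budget to cover it. This cannot be repaired after unblinding.

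**Working it through.** **Inputs from protocol 12.1.** "Power is calculated for the Primary Efficacy Endpoint for the chi-square test using a 2-sided significance level of 0.025". The Week 24 response "is assumed to be 40%, 25%, and 10% for the CTP-543 12 mg, CTP-543 8 mg BID, and placebo groups, respectively". Group sizes are 210, 350 and 140. Stated power is above 99% for 12 mg; for 8 mg it is given as "approximately 94% power for the comparison of CTP-543 8 mg BID versus placebo".

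**1. Reproducing the stated power.** Power = Φ[(d − z·SE0)/SE1], with SE0 from the pooled rate, SE1 from the separate rates, and z = 2.2414 for two-sided 0.025.
- 8 mg: pooled rate (87.5 + 14)/490 = 0.2071; SE0 = √(0.2071 × 0.7929 × 0.01) = 0.04053; SE1 = √(0.1875/350 + 0.09/140) = 0.03433.
- Without continuity correction, d = 0.15, which gives 1.72 and power 95.8%. With it, d = 0.15 − 0.5 × 0.01 = 0.145, which gives 1.58 and power 94.3%. The latter matches the stated 94%.
- 12 mg: above 99.9% either way.
- At two-sided 0.05 (z = 1.96), 8 mg power on the primary becomes 98.0% (uncorrected) or 97.2% (corrected). The most that the transfer can add on the primary is therefore about 2 to 3 points.

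**2. Does a transfer keep family-wise error at or below 0.05?** There are two cases.
- Both sequences contain a true null. Completing either sequence means that a true null in it has already been rejected, so the first error must be made at 0.025. The bound is 0.025 + 0.025 = 0.05.
- Only one sequence contains a true null. Its first true null is tested at no more than 0.05.

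With all nulls true, the correlation from the shared placebo group is √(210/350 × 350/490) = 0.655. Simulated family-wise error is 0.0437 with or without the transfer.

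**3. Can a claim be lost?** No. The completed dose keeps all six, and anything rejected at 0.025 on the other dose is also rejected at 0.05.

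**4. What does it cost?** Simulating a 12 mg dose that works strongly on every endpoint and an 8 mg dose equal to placebo, the chance of rejecting a true 8 mg null is 0.024 now and 0.050 with the transfer. Both count rejections in either direction.

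**5. How large is the gain?** An extra claim needs one dose to win all six steps at 0.025 and the other's first failing p to lie between 0.025 and 0.05. As a guide, a test with 80% power at 0.025 has 87% at 0.05, and one with 60% has 70%.

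The documents give no SPRO rates and no SALT response rates before Week 24, so these are assumptions. The simulations used the planned group sizes, correlated endpoints and unstratified comparisons of proportions, without missing data.
- Run A: SPRO 45/33/15% (12 mg/8 mg/placebo). SALT at Weeks 20, 16, 12 and 8, taking the Week 8 rates of 12%, 7% and 3% in turn: 12 mg 33/25/18/12, 33/25/15/7 and 30/20/10/3%; 8 mg 20/15/10/6, 20/14/8/4 and 18/12/6/2%; placebo 7/5/3/1, 8/6/4/1 and 8/6/3/1%.
- Run B: weak SPRO effect, 25% on 8 mg v 15% on placebo.
- Run C: SPRO as strong as the primary, 40/25/10%; SALT 33/20/7, 25/15/5 and 16/10/3% at Weeks 20, 16 and 12.

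| 12 mg at Week 8 (placebo 1%) | Power of that step alone | 12 mg completes (A / B / C) | Extra protected claim (A / B) | 8 mg SPRO claim, weak (B) | 8 mg SPRO claim, strong (C) |
|---|---|---|---|---|---|
| 12% | 97% | 98 / 99 / 98% | 26 / 23% | 58 → 68% | 93 → 96% |
| 7% | 67% | 67 / 74 / 73% | 20 / 22% | 58 → 66% | 93 → 95% |
| 5% | 40% | C only: 42% | not run | not run | about +1 point |
| 3% | 14% | 8 / 9 / 9% | 2 / 2% | not reported | essentially none |

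In run A the mean number of protected claims, out of 12, rises by 0.52, 0.33 and 0.03 at Week 8 rates of 12%, 7% and 3%.

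**6. The gate.** If both doses must pass the primary and SPRO before either goes on, 12 mg cannot complete until 8 mg has already won SPRO at 0.025. The transfer could then help only the Week 20 to Week 8 claims, and the SPRO gains in the table vanish.

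**The case against.** The strongest reply is that nothing is wrong: an equal split with a fixed sequence per dose is valid, and keeping each dose's error budget to itself is a legitimate conservative choice. That stands.

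A reader might infer that the present rule forgoes claims with no gain at all in error control. The documents do not support that. The 0.05 bound is the same under both rules, but step 4 shows that the present rule roughly halves the attained error for an ineffective dose when the other dose wins everything. That is a real trade-off, although the stated purpose of the split needs only the overall bound.

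A reader might also infer, from power above 99% on the primary, that 12 mg will probably finish its sequence. Primary power says nothing about the sixth step. Protocol 4.4.2 reports Phase 2 separation from placebo from Week 12 and gives nothing for Week 8. If Week 8 response on 12 mg is near 3%, the transfer almost never comes into play.

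Finally, a gain of about 10 points on 8 mg SPRO is tempting to quote. It appears only with a weak assumed SPRO effect and a favourable Week 8 rate, and nothing in the documents shows that 8 mg SPRO power is marginal.

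**Conclusion.** The point holds as one of efficiency. The text lacks a transfer that would preserve the 0.05 family-wise bound, could not lose a protected claim and would sometimes add one. At assumed 12 mg Week 8 rates of 12%, 7% and 3%, an extra claim follows in about 23–26%, 20–22% and 2% of trials. At the two higher rates, the gain on 8 mg SPRO is about 8 to 10 points if its effect is weak and 2 to 3 points if it matches the primary. These sizes rest on assumed SPRO and early SALT rates and on the SAP's dose-by-dose gate. The plan as written is not in error.

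**What to change.** Before unblinding, add to SAP 8.1.4, Figure 1 and protocol 12.4.3: if all six hypotheses of one dose are rejected at two-sided 0.025, the other dose's sequence is tested in the same order at two-sided 0.05. In the same edit, settle the gate before the Week 20 to Week 8 steps as dose by dose, as in the SAP, and list that departure from the protocol in SAP Section 13. State the trade-off openly: error for an ineffective dose can rise from about 0.025 to 0.05 when the other dose wins every step, still within the overall bound.

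The cost is two sentences, a redrawn figure and the gate wording. No patients are added and no existing claim is put at risk.
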